## **9.6 Prior, Concomitant, and Rescue Medications and Therapies**

All medications recorded on the concomitant medications case report form page will be coded using the World Health Organization Drug Dictionary Enhanced (WHO-DDE), September 2016 version. Medications will be listed and summarized by Anatomical Therapeutic Chemical (ATC) level 4 and generic name. All prior and concomitant medications, all rescue medications, and epinephrine medications will be listed separately.

Prior medications are defined as those taken prior to the date of the first dose of study product on day 1 (ie, medication end date is prior to the date of first dose of study product).

Concomitant medications are medications taken any time during the active treatment period. Concomitant medications also include medications recorded for which dosing began after the last dose of randomized study treatment. As needed (PRN) medications taken during the active treatment period will be considered concomitant medications. If it cannot be determined whether a medication was received prior to the start of study product dosing due to partial or missing medication start and/or end dates, it will be considered a concomitant medication.

Rescue medications are any medication used to treat symptoms of an acute allergic reaction as identified on the concomitant medication case report form. Each use of a rescue medication during study treatment should be associated with a corresponding adverse event. Prior medications and concomitant medications including rescue medications will be summarized for the safety population by age group (4-11 years, 12-17 years, 4-17 years), treatment group (AR101, placebo), ATC class, and generic name. Subjects will be counted no more than once per generic name and no more than once per ATC level 4 in the summary.

Rescue medications will be summarized for the safety population by age group (4-11 years, 12-17 years, 4-17 years), treatment group (AR101, placebo), ATC class and generic name for the following study periods: initial escalation, up-dosing, 300 mg QD, and overall.

Concomitant non-drug therapies will be listed by subject.

## **9.7 Efficacy Analyses**

ARC007 is a study to assess safety and tolerability of AR101. As such, all study endpoints are considered safety endpoints and no efficacy analyses will be performed.

## **9.8 Safety Analyses**

Safety will be assessed by all the endpoints defined in [Section 4](#).

Safety data will be summarized descriptively and the safety population will be used for all summaries of safety parameters, unless otherwise noted. Safety listings will include all randomized subjects sorted by treatment group (AR101 then placebo).

### **9.8.1 Adverse Events**

All adverse events recorded on the adverse event case report form, symptoms recorded on the allergic adverse events case report form, and symptoms recorded on the in-clinic dosing case report will be summarized together.

If symptoms are recorded as part of an anaphylaxis reaction as reported on the Allergic AE or in-clinic dosing form, only the single anaphylaxis reaction event will be summarized and not the individual symptoms.

All reported adverse events will be classified into SOC and preferred term using MedDRA version 19.1.

Treatment-emergent adverse events are defined as those adverse events with onset after the first dose of study product. Adverse events with onset prior to first dose of study product will be included in subject listings, but not summarized. Treatment-emergent adverse events and non-treatment-emergent adverse events will be listed separately. Treatment-emergent adverse events will be summarized for the safety population by age group (4-11 years, 12-17 years, 4-17 years), treatment group (AR101, placebo), and by study period as follows:

- Initial escalation: All events beginning after the first dose of study product on day 1 and prior to the first administration of study product at home. To avoid gaps between study periods, the first administration of study product at home is assumed to be the day after at-home study product was dispensed at Initial Escalation Day 2.
- Up-dosing: All events beginning after the first administration of study product at home during up-dosing and prior to the first dose of 300 mg at home. To avoid gaps between study periods, the first administration of 300 mg at-home dose is assumed to be the day after the clinic visit where 300 mg dose was first tolerated and at-home 300 mg study product was dispensed.
- 300 mg QD: All events beginning after the first dose of 300 mg at home and prior to exit from the study.
- Overall: Across initial escalation, up-dosing, and 300 mg QD periods (first dose to last dose).

Summaries displayed by SOC and preferred terms will be ordered by descending incidence of SOC and preferred term within each SOC. Summaries displayed by preferred term only will be ordered by descending incidence of preferred term. Summaries of the following types will be presented:

- Overall summary of number of unique treatment-emergent adverse events and treatment-emergent serious adverse events, subject incidence of treatment-emergent adverse events and treatment-emergent serious adverse events meeting various criteria, and exposure-adjusted incidence rates of treatment-emergent adverse events and treatment-emergent serious adverse events meeting various criteria, where exposure incidence rates are defined as the total number of events divided by the total number of subject-years at risk; the total number of subject-years at risk is defined as total number of days for all subjects in the study period divided by 365.25.
- Subject incidence of treatment-emergent adverse events by SOC and preferred term.
- Subject incidence of treatment-emergent adverse events by preferred term.
- Exposure-adjusted event rates for the most frequent treatment-emergent adverse events (ie, treatment-emergent adverse events occurring in  $\geq 5\%$  of the safety population) by preferred term.
- Subject incidence of treatment-emergent adverse events by severity grade, SOC, and preferred term.
- Subject incidence of treatment-emergent adverse events related to study product by SOC and preferred term.
- Exposure-adjusted event rates for the most frequent treatment-emergent adverse events related to study product (ie, related treatment-emergent adverse events occurring in  $\geq 5\%$  of the safety population) by preferred term.
- Subject incidence of grade  $\geq 3$  severity treatment-emergent adverse events by SOC and preferred term.
- Subject incidence of grade  $\geq 3$  severity treatment-emergent adverse events related to study product by SOC and preferred term.
- Subject incidence of serious adverse events by SOC and preferred term.
- Subject incidence of treatment-emergent adverse events leading to discontinuation of study product by SOC and preferred term.
- Subject incidence of treatment-emergent adverse events associated with the use of epinephrine by SOC and preferred term.
- Subject incidence of hypersensitivity treatment-emergent adverse events by SOC and preferred term, where hypersensitivity treatment-emergent adverse events are those treatment-emergent adverse events from the allergic adverse event and in-clinic dosing case report forms.

- Subject incidence of hypersensitivity treatment-emergent adverse events related to study product by SOC and preferred term.
- Exposure-adjusted event rates for hypersensitivity treatment-emergent adverse events by preferred term.
- Subject incidence of treatment-emergent adverse events associated with a non-study product food allergen exposure by SOC, and preferred term.
- Subject incidence of treatment-emergent adverse events leading to early discontinuation by SOC and preferred term.
- Subject incidence of treatment-emergent adverse events with onset < 90 minutes after study product dosing at the study site by SOC and preferred term.

At each level of summarization (eg, any adverse event, SOC, and preferred term), subjects experiencing more than 1 treatment-emergent adverse event will be counted only once within each study period. In the summary of treatment-emergent adverse events by severity grade, subjects will be counted once at the highest severity reported at each level of summarization. Adverse event data will be presented in data listings by age group, treatment group, subject, study period, and event. Treatment-emergent adverse events; serious adverse events; severe, life-threatening, or fatal adverse events; and adverse events leading to discontinuation, reduction, or interruption of the study product will be presented in separate data listings.

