### 4.1 Primary Endpoint

The primary endpoint is the frequency of treatment-emergent adverse events, including serious adverse events, during the overall study period.

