## 7 DEFINITIONS, DERIVATIONS, AND CONVENTIONS

### 7.1 Definitions and Derivations

- Study day is calculated as (assessment date – first dose date + 1) for assessments and visits performed on or after the first dose date, and (assessment date – first dose date) for assessments and visits prior to the first dose date.
- Baseline is defined as the last nonmissing value prior to the first dose of randomized study treatment in ARC007.
- Change from baseline is calculated as the observed value after the first dose – baseline value.
- The screening period is defined as the time beginning with the date and time of informed consent through the day prior to randomization.
- Initial escalation is defined as the time beginning with the date and time of the first dose of randomized study product at the study site and ending with the date of the last dose of randomized study product taken prior to up-dosing.
- Up-dosing is defined as the time beginning with the date and time of the first dose of study product at 3 mg at home, and ending with the date and time of first dose at

300 mg at the study site. Up-dosing will be approximately 20 weeks in duration, but may be extended to a maximum of 40 weeks to accommodate dose reductions and re-escalations, if necessary.

- A 300 mg QD period will be defined as the time beginning with the date and time of the first dose of study product at 300 mg at home and ending with the date of the last dose of study product. This period will be ideally approximately 2 weeks in duration at the end of ARC007, but dosing may continue up to a maximum of 48 weeks after day 1 to ensure tolerability of 300 mg prior to exiting ARC007. Some subjects continued to receive 300 mg doses in ARC007 after the expected rollover date while waiting for activation of ARC008 or ARC011 at the study site. The 300 mg doses as a result of the rollover delay will be included in the 300 mg QD period.

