### 9.5 Extent of Exposure and Compliance

Study treatment exposure will be summarized for the safety population by age group (4-11 years, 12-17 years, 4-17 years), treatment group (AR101, placebo) and study period (initial escalation, up-dosing, 300 mg QD, and overall).

First and last dose dates for each study period will be identified as follows:

Study Period	First Dose Date	Last Dose Date
Initial escalation	Date of first dose at the study site on initial escalation day 1	Date of last dose at initial escalation day 1 or day 2 at the study site
Up-dosing	The day following the date study product was dispensed at initial escalation day 2	Date of first dose of 300 mg at the end of the up-dosing 300 mg visit if dose is tolerated and subject continues to at-home 300 mg QD dosing. If first in-clinic 300 mg dose is not tolerated and dose is immediately reduced, the last dose date of up-dosing will be when the first in-clinic 300 mg dose is tolerated and subject continues to at-home 300 mg QD dosing. For subjects who do not reach the 300 mg dose, the latest of the last dose during up-dosing at the study site and the last dose at home
300 mg QD	Date of first dose of study product of 300 mg at home. This is defined as the day following the first in-clinic visit where the 300 mg dose was tolerated and 300 mg study product was first dispensed.	Date of last dose of study product for subjects who enter 300 mg QD study period
Overall	Date of first dose at the study site on initial escalation day 1	Last dose of study product prior to exit visit in ARC007

The total amount of study product consumed will be calculated as the sum of doses at the study site plus the sum of doses taken at home as recorded in the dosing diary.

The following calculations of study product exposure will be made and summarized:

- Duration of exposure (in days and in months): calculated as the date of the last dose of study product minus the date of the first dose of study product plus 1 during the study period, except for initial escalation, the duration of exposure will only be 1 or 2 days depending on whether study product was taken on initial escalation day 1 and initial escalation day 2. Duration of exposure will be summarized using descriptive statistics for continuous endpoints and categorically by 28-day increments for the overall treatment period:  $\leq 28$  days, 29–56 days, ... 337–364 days, and  $> 364$  days.

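### SAP 9.8.1 gives Overall, the window of the primary endpoint, two different end dates (study exit and last dose) and does not say where a period ends for a subject who stops within it

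*SAP*

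**What the plan says.** SAP 4.1 sets the endpoint: "The primary endpoint is the frequency of treatment-emergent adverse events, including serious adverse events, during the overall study period". SAP 9.8.1 then defines the counting windows. Overall is "Overall: Across initial escalation, up-dosing, and 300 mg QD periods (first dose to last dose" (closing bracket omitted here). The last component is "300 mg QD: All events beginning after the first dose of 300 mg at home and prior to exit from the study". Initial escalation takes in "All events beginning after the first dose of study product on day 1 and prior to the first administration of study product at home", and up-dosing runs from the first dose "at home during up-dosing and prior to the first dose of 300 mg at home". A TEAE is any event with onset after the first dose; no end is given.

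Two other sections date the same periods. SAP 7.1 has the 300 mg QD period starting with the first dose "at 300 mg at home and ending with the date of the last dose of study product". SAP 9.5, for exposure, closes up-dosing for subjects who do not reach 300 mg at "the latest of the last dose during up-dosing at the study site and the last dose at home", limits initial escalation to 1 or 2 days, and ends Overall at the "Last dose of study product prior to exit visit in ARC007".

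For exposure-adjusted rates, SAP 9.8.1 divides events by the days of all subjects in the study period over 365.25. It does not say whether those are the 9.5 days or the days of the AE windows.

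**The concern.** A programmer can build the primary endpoint table in two ways from one sentence. If the bracket governs, events after last dose leave Overall although the TEAE definition and the period columns admit them, so the columns need not reconcile. If the word before the bracket governs, they stay in.

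The choice bears on subjects who stop early, who matter most for tolerability, and probably on AR101 more than placebo. It also reaches the secondary objective of treatment-related events by study period and the secondary endpoint of hypersensitivity events in up-dosing normalized for treatment duration. The study is descriptive, so the counting rule largely is the analysis.

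**Working it through.** The documents give no figure that depends on this point, so there is nothing to reproduce. I compared the definitions and then sized the disputed time.

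**Where each period ends**

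| Period | SAP 7.1 | SAP 9.5 (exposure) | SAP 9.8.1 (events) |
|---|---|---|---|
| Initial escalation | last dose before up-dosing | last site dose, Day 1 or 2 | first home dose |
| Up-dosing | first 300 mg site dose; no rule for those who never reach it | first tolerated 300 mg site dose; otherwise last dose | first 300 mg home dose; no rule for those who never reach it |
| 300 mg QD | last dose | last dose | study exit |
| Overall | not defined | last dose before the exit visit | union of the three, and also last dose |

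The firmest case is a subject who stops during 300 mg QD. An event on day 5 after last dose is before exit, so it belongs to the 300 mg QD column; it is after last dose, so the bracket removes it from Overall. Such events are collected: Protocol 7.6 asks for events found after dosing stops and before the Early Discontinuation Visit, which Protocol 6.8 puts at 14 days, minus 3 to plus 7 (11 to 21). For completers who exit on schedule, last dose and exit nearly coincide.

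**Disputed time, AR101 arm** (illustration; the documents give no ARC007 discontinuation rate)

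- Arm size: 500 × 2/3 = 333.
- Early stopping, borrowed from ARC001 (Protocol 1.2.1): 6/29 = 20.7%, exact 95% CI 8.0% to 39.7%. Times 333: 69 subjects (27 to 132).
- Disputed time: 69 × 14 / 365.25 = 2.6 subject-years. With 11 and 21 days: 2.1 and 4.0. With 27 and 132 subjects at 14 days: 1.0 and 5.1.
- Dosing time, assuming stoppers are dosed for half the period: at 22 weeks (264 × 154 + 69 × 77) / 365.25 = 125.9 subject-years; at 48 weeks (264 × 336 + 69 × 168) / 365.25 = 274.6.
- Ratio: 2.64/125.9 = 2.1%; 2.64/274.6 = 1.0%. Over the CI: 1.03/293.9 = 0.35% to 5.06/112.6 = 4.5%.

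**By period**

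- Up-dosing, if all 69 stop there: 69 × 14 = 966 days, over 264 × 140 + 69 × 70 = 41,790 days (2.3%) at 20 weeks, or 264 × 280 + 69 × 140 = 83,580 days (1.2%) at 40 weeks.
- Initial escalation: at most 333 × 2 = 666 dosing days. At assumed failure rates of 1%, 3% and 5% (3, 10 and 17 subjects), a window left open 14 days adds 42, 140 or 238 days, which is 6%, 21% or 36% of 666.

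**Any-TEAE incidence.** A subject changes status only if the first TEAE begins after last dose. ARC001 incidence was 97% on AR101 and 85% on placebo. If 97% of the 69 stoppers already had an on-treatment TEAE, 0.03 × 69 = 2.1 subjects could change, or 2.1/333 = 0.6 percentage points at most.

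**By arm.** ARC001 had 26 treated placebo subjects, and 26 subjects who had completed placebo were dosed in ARC002 (Protocol 1.2.2). Placebo withdrawals therefore appear to be 0 of 26 (upper 95% limit 13.2%), which suggests that the disputed time falls mainly on AR101.

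**The case against.** The best defence is that one stray bracket is the whole fault. SAP 9.8.1 says twice that its windows are set to avoid gaps between periods. The natural reading is then exhaustive: a subject who never takes a home dose stays in initial escalation, one who never takes 300 mg at home stays in up-dosing, and study exit ends both. Every TEAE then has a period, and Overall is their union. SAP 9.5 is about exposure and need not match. No hypothesis test is planned, and TEAEs are listed by study period in any case.

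Much of this stands. The text supports reading the early-stopper windows as open until exit, so a reader who infers that these windows cannot be closed at all goes too far. A reader might also infer that the exposure-adjusted rates are wrong. That follows only if the denominator is the 9.5 days, which the SAP does not say. The borrowed 6/29 is weak too: ARC001 took ages 4 to 26 and had a maintenance period.

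The defence does not remove the conflict. The exhaustive reading contradicts the bracket, and SAP 7.1 and 9.8.1 still end 300 mg QD on different dates. SAP 9.5 cannot settle it, because 9.8.1 neither cites it nor matches it.

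**Conclusion.** The definition of the primary endpoint's window contradicts itself and should be corrected before the tables are programmed. Under the bracket, events after last dose in early discontinuers can appear in a period column and not in Overall. If the rate denominators use the 9.5 days, period rates also count events without their person-time.

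The size is modest: about 1% to 2% of AR101 dosing time at 6/29 stopping and a 14-day interval, and 0.35% to 4.5% over the CI of that rate. These are days, not events; the documents give no event rate after last dose, so no change in an event rate can be computed. Any-TEAE incidence is likely to move very little. Preferred-term counts in early discontinuers and initial escalation rates are more sensitive, the latter under assumed failure rates.

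A reader might infer that safety events are lost from the report. The documents do not support that: SAP 9.8.1 lists TEAEs and serious adverse events separately. What is undefined is where they are counted.

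**What to change.** In SAP 9.8.1:

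- Delete the bracket. Define Overall for TEAE counting as first dose through the subject's actual exit from ARC007, never earlier than last dose and before any ARC008 or ARC011 dose.
- Define actual exit as the Early Discontinuation Visit or the final exit visit. For subjects kept on blinded treatment while awaiting rollover, it is the final unscheduled visit (Protocol 6.4). Ending Overall at the scheduled Exit Visit would cut off events while these subjects are still dosing, and SAP 7.1 counts those doses in 300 mg QD.
- State one end for each period for subjects who stop within it. Study exit fits the gap-free wording and keeps Overall equal to the sum of its parts.
- Compute days at risk over exactly the window used to count events.
- Also give on-treatment rates (to last dose), overall and by period, so that off-drug days do not dilute the period rates.

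Align SAP 7.1, including the end of up-dosing, which it puts at the first 300 mg site dose and 9.8.1 at the first 300 mg home dose.

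Two additions are optional: a cap at last dose plus 21 days where no visit occurs, and a separate post-treatment column with periods closed at last dose. The column would move a delayed reaction starting the next day out of the dosing period that preceded it.

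The cost is SAP wording, minor reprogramming on events already collected, and about 1% to 2% more AR101 person-time in Overall at 6/29 stopping. The final analysis is not delayed.

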## 5 SAMPLE SIZE CONSIDERATIONS

ARC007 is a safety study designed to add critical placebo-controlled data to the ongoing safety database of AR101. As such, there are no efficacy endpoints in the study, no specific efficacy-related hypotheses to be tested, and no prospective sample size calculations performed related to the power to detect a prespecified treatment effect size. A sample size of up to 500 subjects randomized in a 2:1 ratio to AR101 or placebo, along with subjects enrolled in other studies in the clinical program was to provide a sufficient number of subjects to fulfill the regulatory requirement for data on at least 600 subjects treated with AR101 at 300 mg/day for 6 months. Randomization was stratified by age group (4-11 years and 12-17 years).

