## 6 ANALYSIS POPULATION

### 6.1 Safety Population

The safety population is defined as all subjects who received at least 1 dose of randomized study treatment in ARC007. Subjects will be analyzed according to treatment received.

The safety population of pediatric subjects aged 4 to 17 years will be the population for all analyses unless otherwise specified.

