## 7.2 Programming Conventions

Unless stated otherwise, the term “descriptive statistics” refers to the number of subjects (n), mean, median, standard deviation, minimum, and maximum for continuous variables and frequencies and percentages for categorical variables.

Unless specified otherwise, the denominator for percentages for categorical data will be based on the number of subjects or observations with nonmissing data appropriate for summary purposes. The denominator for percentages for incidence data (such as adverse events) will be based on the number of subjects in the analysis population “at risk”.

Minimum and maximum values will be presented at the precision of the original value, means, medians will be rounded to 1 decimal place greater than the precision of the original value, standard deviations and standard errors will be rounded to 2 decimal places greater than the precision of the original value. Percentages will be rounded to 1 decimal place. Percentages that round down to 0 or up to 100% will be displayed as “< 0.1%” and “> 99.9%”, respectively.

All summary tables will be presented by treatment group displayed as AR101 and placebo. For disposition, demographic, and other summaries of baseline and history data, a total column for both treatment groups combined will be included.

All relevant data collected in the database will be included in data listings and sorted by treatment group, subject number, and visit and time point as appropriate. The treatment group will be displayed by AR101 then placebo.

Unscheduled visits will be listed but not included in by-visit summaries. Results from unscheduled visits may be used as baseline values and for other derivations not tied to visit names (for example, unscheduled visits are included in the determination of worst postbaseline values for laboratory shift tables).

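### Two of the three preferred-term exposure-adjusted rate tables apply their 5% cut to both arms pooled, so at 2:1 a term needs about 7.5% minus half its placebo incidence on AR101 to qualify

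*SAP*

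**What the plan says.** SAP 9.8.1 lists three tables of exposure-adjusted rates by preferred term.

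- All treatment-emergent adverse events (TEAEs): "Exposure-adjusted event rates for the most frequent treatment-emergent adverse events (ie, treatment-emergent adverse events occurring in" at least 5% of the safety population.
- Related TEAEs: "Exposure-adjusted event rates for the most frequent treatment-emergent adverse events related to study product", again kept only when the related term reaches 5% of the safety population.
- Hypersensitivity: "Exposure-adjusted event rates for hypersensitivity treatment-emergent adverse events by preferred term", with no cut. The scope is set earlier in the same list: "hypersensitivity treatment-emergent adverse events are those treatment-emergent adverse events from the allergic adverse event and in-clinic dosing case report forms".

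The denominator comes from SAP 6.1: "The safety population is defined as all subjects who received at least 1 dose of randomized study treatment in ARC007". Both arms are in it. The size and allocation are in SAP 5: "A sample size of up to 500 subjects randomized in a 2:1 ratio to AR101 or placebo".

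Subject incidence has no cut. The list includes "Subject incidence of treatment-emergent adverse events by preferred term" and the corresponding table for related events by system organ class and preferred term. SAP 7.2 sets the layout: "All summary tables will be presented by treatment group displayed as AR101 and placebo". SAP 9.8.1 also breaks TEAE summaries down by age group and study period, but does not say at which of these levels the 5% is evaluated.

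**The concern.** A cut on the pooled population dilutes an effect of the active product. Placebo subjects who never have the event still count in the denominator, so a term confined to AR101 must exceed 5% on AR101 by a clear margin before it is kept. The dilution should be greatest in the related-event table, because related events are expected mainly on AR101.

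The exposure-adjusted tables carry information that the incidence tables do not. They divide all events by subject-years, whereas the incidence tables count a subject once per period. A term that misses the cut loses both the adjustment for time on treatment and the information on recurrence. Time on treatment can plausibly differ by arm. The protocol synopsis gives dosing of typically 22 to 48 weeks, with possible extension, and Protocol 1.2.1 reports that 4 of 29 AR101 subjects (14%) and no placebo subject stopped for an adverse event in ARC001.

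The related-event table also bears on the secondary objective in SAP 3.2 of describing how often treatment-related events occur in each study period.

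**Working it through.** The plan states no figure for the incidence an arm must reach, so there is nothing to reproduce. The check is direct arithmetic.

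**Inputs.** N = 500 at 2:1 (SAP 5), taken as 333 AR101 and 167 placebo, all dosed. Cut: 5% of the safety population (SAP 9.8.1, 6.1). The placebo incidence of a given term is not in the documents and is varied from 0% to 5% as an assumption.

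**Count needed.** 0.05 × 500 = 25 subjects across both arms.

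**AR101 incidence needed.** Let a and p be the AR101 and placebo incidences. The term is kept when a × (2N/3) + p × (N/3) ≥ 0.05 × N, that is, when a ≥ 0.075 − p/2.

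| Placebo incidence | AR101 incidence needed |
|---|---|
| 0% | 7.5% |
| 1% | 7.0% |
| 2% | 6.5% |
| 3% | 6.0% |
| 4% | 5.5% |
| 5% | 5.0% |

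In whole subjects with placebo at zero, 25/333 = 7.5% is kept. A term with 24/333 = 7.2% on AR101 is 24/500 = 4.8% pooled and is dropped.

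**Smaller enrolment.** The 500 is an upper limit. At N = 450 the count is 22.5, rounded up to 23, and 23/300 = 7.7%. At N = 400 it is 20, and 20/267 = 7.5%. The result barely depends on N.

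**Chance that a term is tabulated.** Take placebo at zero and the AR101 count as binomial with n = 333. The pooled rule needs at least 25. An either-arm rule needs at least 17, since 0.05 × 333 = 16.65 and 17/333 = 5.1%.

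| True AR101 incidence | Pooled rule | Either-arm rule |
|---|---|---|
| 5% | 3% | 50% |
| 6% | 15% | 79% |
| 7% | 39% | 93% |
| 8% | 66% | 98.5% |

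**Which events are exposed to the cut.**

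- Events from the allergic adverse event form or the in-clinic dosing form: their rate by preferred term appears in the hypersensitivity table at any incidence, but related and unrelated events are counted together. Related hypersensitivity events are listed for subject incidence only.
- Events recorded only on the general adverse event form: no rate by preferred term unless the term passes the pooled cut. Protocol 7.2 has sites mark each symptom as allergic or not, and Protocol 6.5.3.2 separates chronic or recurrent symptoms, most often gastrointestinal, from acute dosing symptoms. A gastrointestinal event not entered as allergic falls in this group.

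**The case against.** The strongest reply is that the reactions that matter most are already covered. Protocol 1.4.1 describes adverse events of oral immunotherapy as almost entirely allergic, and SAP 9.8.7 says that the allergic adverse event form holds all dose-related symptoms at home. With the in-clinic form added, the uncut hypersensitivity table reaches the main class of AR101 reactions. This stands. A reader might infer from the 7.5% that any AR101-specific reaction below that level goes without an exposure-adjusted rate. The documents do not support that, because one of the three rate tables has no cut.

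Other parts of the reply also stand. The 7.5% is the zero-placebo extreme, and non-allergic terms are those most likely to have some placebo background. A reader might also say that the plan breaks its own 5% standard. It does not: its standard is 5% of the safety population, and it sets none within an arm. For terms below the cut, incidence by arm, event listings and exposure duration by arm (SAP 9.5) all remain, as do the overall exposure-adjusted rates of TEAEs and serious TEAEs.

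It could also be argued that the 5% is meant within each treatment group, since TEAEs are summarized that way. The SAP does not say so, and its wording points to the pooled population.

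The reply does not remove the gap. The hypersensitivity table does not isolate related events, so the cut table is the only listed summary of rates by preferred term for related events. Nor does it reach events held only on the general form.

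**Conclusion.** The point holds in limited form, as a cheap improvement. On the literal text, two of the three rate tables use a pooled cut. At 2:1 it requires about 7.5% minus half the placebo incidence on AR101: 7.5% for a term absent on placebo, 6.5% at 2%. For a true 6% on AR101 and 0% on placebo, the chance of being tabulated is 15%, against 79% under an either-arm rule.

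The loss is confined to exposure-adjusted rates by preferred term, for related events as such and for events recorded only on the general adverse event form. The study is descriptive, and the primary endpoint's incidence tables are unaffected. The figures assume that the 5% is evaluated on all dosed subjects over the whole study. The probabilities also assume 333 AR101 subjects and no placebo cases.

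**What to change.** In both bullets of SAP 9.8.1 that carry the cut, change the condition to: *occurring in ≥ 5% of subjects in either treatment group (safety population, ages 4–17 years, overall period)*. The set of terms is then fixed once and carried through every age-group and study-period table. If a per-arm rule was already intended, the same wording settles it.

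The cost is one phrase and some additional rows. A few will be sparse: 0.05 × 167 = 8.35, so a term seen in 9 placebo subjects (9/167 = 5.4%) would qualify on placebo alone, and its rates will be unstable in the smaller subgroups. No data collection or other table changes.
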